5.6.2. Adverse Events

All AEs will be coded using the MedDRA coding dictionary version 27.0 and displayed in tables and data listings using system organ class (SOC) and preferred term (PT).

Analyses of AEs will be performed for those events that are considered treatment-emergent adverse events (TEAEs), defined as those with initial onset or increasing in severity after the first dose of study treatment through 30 days after the last dose of study treatment. The imputation of partial/missing dates is described in Section 4.9.1.

Treatment-related TEAEs are defined as a TEAE that was considered by the Investigator to be related to the study treatment. If “Relationship to Study Treatment” is missing, it will be imputed as related in summary tables.

AE grade refers to the severity of the AE. The Common Terminology Criteria for Adverse Events (CTCAE) version 5.0 displays Grades 1 through 5 with unique clinical descriptions of severity for each AE based on this general guideline:

- Grade 1 Mild; asymptomatic or mild symptoms; clinical or diagnostic observations only; treatment not indicated.
- Grade 2 Moderate; minimal, local or noninvasive intervention indicated; limiting age-appropriate instrumental Activities of Daily Living (ADL).
- Grade 3 Severe or medically significant but not immediately life-threatening; hospitalization or prolongation of hospitalization indicated; disabling; limiting self-care ADL.
- Grade 4 Life-threatening consequences; urgent intervention indicated.
- Grade 5 Death related to AE.

An event is defined as ‘serious’ when it meets at least 1 of the predefined outcomes as described in the definition of an SAE (Protocol Appendix A5-1.3), not when it is rated as severe.

A summary of TEAEs will include the number and percentage of participants who experience at least one of the following. The total number of events will also be reported.

- TEAEs

- TEAEs related to study treatment
- Serious TEAEs
- Serious TEAEs related to study treatment
- Serious TEAEs by maximum severity (Grade)
- TEAEs with CTCAE grade ≥ 3
- TEAEs with CTCAE grade ≥ 3 related to study treatment
- TEAEs by maximum severity (Grade)
- TEAEs leading to early discontinuation from study treatment
- TEAEs leading to early discontinuation from study treatment related to study treatment
- TEAEs leading to dose reduction
- TEAEs leading to dose reduction related to study treatment
- TEAEs leading to dose interruption
- TEAEs leading to dose interruption related to study treatment
- TEAEs leading to dose reduction or interruption
- TEAEs leading to dose reduction or interruption related to study treatment
- TEAEs leading to death
- TEAEs leading to death related to study treatment
- TEAEs by cycle of onset

In each tabulation of TEAEs, each participant will contribute only once (i.e., the most related occurrence, or the most intense occurrence, or the first cycle of onset) to each of the participant incidence rates in the descriptive analysis, regardless of the number of episodes.

The above categories will also be presented in tables summarizing SOC and PT, and sorted by descending frequency. If a participant experiences multiple AEs under the same PT (or SOC), the participant will be counted only once for that PT (or SOC). The number of events of each type will be displayed alongside associated participant incidence percentages.

A TEAE summary by PT only and sorted by descending frequency will also be produced.

All AEs will be listed in participant data listings. By-participant listings will also be provided for the following: TEAEs leading to death, serious adverse events, TEAEs leading to study treatment withdrawn, and TEAE leading to discontinuation from study.

5.6.3. Safety Topics of Special Interest

Safety topics of special interest have been identified based on review of safety data from prior studies with nirogacestat and include additional AEs beyond those specified in Protocol Section 11.3.1 as adverse events of special interest (AESIs). These safety topics of interest, including AESIs determined by the investigators for this study, will be summarized on separate tables. These safety topics, including AESIs, are defined for analysis purposes in different ways, including by using standardized MedDRA queries (SMQ) or customized MedDRA queries, and whether an investigator determined that an event was an AESI.

Unless specified otherwise, the incidence of AESIs based on the investigator's determination will be summarized by SOC and PT in tables and listed separately in participant data listings, and those by using defined lists of specific MedDRA PTs without regard to the investigator's designation of the reported event as an AESI will be summarized similarly.

For the safety topics of special interest (including AESIs) defined using standardized MedDRA queries (SMQ) or customized MedDRA queries, the specific MedDRA PTs for inclusion are all listed in Appendix 8.4 under the following groups. Safety topics for which narrow and broad terms are identified, only narrow terms are used for summary tables. The safety topics will be summarized by SOC and PT based on the Safety Analysis Set.

- Hypersensitivity
- Skin Disorder and Rash
- Hepatotoxicity
- Electrolyte Disorder
- Non-melanoma Skin Cancer
- Musculoskeletal Disorders
- Bone Fractures
- Mucositis/Stomatitis

- Hematologic Disorders
- Opportunistic Infections
- Central Nervous System Vascular Disorders
- Embolic and Thrombotic Events
- Cardiac Rhythm Disturbances
- Upper Respiratory Tract Infections
- Diarrhea

In addition to the summaries by SOC and PT as described above, separate summaries for concomitant medication use will be presented for the following safety topics:

- Hypophosphataemia (A subset of Electrolyte Disorder terms)
- Upper Respiratory Tract Infection
- Diarrhea
- Skin and Subcutaneous Rash (Broad and Narrow; a subset of Skin Disorder and Rash terms)
- Skin and Subcutaneous Rash (Narrow; a subset of Skin Disorder and Rash terms)

The number and percentage of participants with concomitant medication used for each safety topic of special interest will be presented by ATC Classification, Preferred Term and Grade (1-2 vs. ≥ 3). The following will be also summarized:

- Number and percentage of participants with the safety topic of special interest
- Time to Onset of First Instance of the safety topic of special interest (days)
- Duration of the safety topic of special interest (days) for each event
- Time from onset of first instance of the safety topic of special interest to resolution of last event
- Number of participants with the safety topic of special interest by outcome, grade (1-2 vs. ≥ 3), and dose modification (if any)
- Number and percentage of participants with concomitant medication use for the safety topic of special interest
- Duration of concomitant medication use for the safety topic of special interest (days)

If an adverse event is ongoing, the end date will be imputed as the data cut-off date for the duration calculation. The duration of concomitant medication use is defined as the number days a participant took medications for the safety topic of special interest. If multiple concomitant medications are taken on a given day, that day will be counted once in the sum. If a medication is ongoing, the end date will be imputed as the last visit date + 28 days (if not before the medication start date), or the study treatment end date if unavailable.

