**Table 9: Adverse Events of Special Interest (AESI)**

Skin Rash (reported as AESI if clinically significant Grade 2 and all Grade <math>\geq 3</math>. Per CTCAE v5.0)
Maculopapular rash
Pruritic rash
Erythematous rash
Folliculitis
Hidradenitis suppurativa
Elevated Liver Enzymes (reported as AESI if Grade <math>\geq 2</math>, per CTCAE v5.0)
AST
ALT
Alkaline Phosphatase
Total bilirubin
Electrolyte Insufficiency (reported as AESI if Grade <math>\geq 3</math>, per CTCAE v5.0)
Hypophosphatemia
Hypokalemia
Hypomagnesemia
Drug Reactions (reported as AESI for any grade)
Allergic reaction
Anaphylaxis
(Drug) hypersensitivity
Ovarian Toxicity (reported as AESI for any grade)
Ovarian dysfunction
Ovarian disorder
Amenorrhea
Oligomenorrhea
Premature menopause
Ovarian failure
Skin Cancer (reported as AESI for any grade)
Basal cell carcinoma
Squamous cell carcinoma (of skin)
Keratoacanthoma
Actinic keratosis
Any other skin cancer

AESI = Adverse Event of Special Interest; ALT = Alanine aminotransferase; AST = Aspartate aminotransferase; CTCAE = Common Terminology Criteria for Adverse Events

Participants reporting AEs/AESIs/SAEs of ovarian toxicity will have hormone levels assessed every 3 months until event resolution (or for at least 90 days after discontinuing study treatment).

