8.4. Safety Topics of Special Interest Preferred Terms

This appendix outlines the definition of treatment-emergent AESIs. Additional attention will specifically be given to the safety topics of special interest identified using SMQ or customized MedDRA queries based on MedDRA version 27.0.

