Biliary cirrhosis	Increased liver stiffness

Biliary fibrosis	International normalised ratio abnormal
Bilirubin conjugated abnormal	International normalised ratio increased
Bilirubin conjugated increased	Intestinal varices
Bilirubin excretion disorder	Intestinal varices haemorrhage
Bilirubin urine present	Intrahepatic portal hepatic venous fistula
Biopsy liver abnormal	Ischaemic hepatitis
Blood alkaline phosphatase abnormal	Jaundice
Blood alkaline phosphatase increased	Jaundice cholestatic
Blood bilirubin abnormal	Jaundice hepatocellular
Blood bilirubin increased	Kayser-Fleischer ring
Blood bilirubin unconjugated increased	Leucine aminopeptidase increased
Blood cholinesterase abnormal	Liver and pancreas transplant rejection
Blood cholinesterase decreased	Mixed liver injury
Blood fibrinogen abnormal	Ocular icterus
Blood fibrinogen decreased	Parenteral nutrition associated liver disease
Blood thrombin abnormal	Liver carcinoma ruptured
Blood thrombin decreased	Liver dialysis
Blood thromboplastin abnormal	Liver disorder
Blood thromboplastin decreased	Liver injury
Bromosulphthalein test abnormal	Liver-kidney microsomal antibody positive ¹
Cardiohepatic syndrome	Liver operation
Child-Pugh-Turcotte score abnormal	Liver sarcoidosis
Child-Pugh-Turcotte score increased	Liver transplant
Cholaemia	Liver transplant failure
Cholangiosarcoma	Liver transplant rejection
Cholestasis	Lupoid hepatic cirrhosis
Cholestatic liver injury	Lupus hepatitis

Cholestatic pruritus	Mixed hepatocellular cholangiocarcinoma
Chronic graft versus host disease in liver	Multivisceral transplantation
Chronic hepatic failure	Nodular regenerative hyperplasia
Chronic hepatitis	Nonalcoholic fatty liver disease
Coagulation factor decreased	Non-alcoholic steatohepatitis
Coagulation factor IX level abnormal	Non-cirrhotic portal hypertension
Coagulation factor IX level decreased	Oedema due to hepatic disease
Coagulation factor V level abnormal	Oesophageal varices haemorrhage
Coagulation factor V level decreased	Peripancreatic varices
Coagulation factor VII level abnormal	Peritoneovenous shunt
Coagulation factor VII level decreased	Portal fibrosis
Coagulation factor X level abnormal	Portal hypertension
Coagulation factor X level decreased	Portal hypertensive colopathy
Coma hepatic	Portal hypertensive enteropathy
Complications of transplanted liver	Portal hypertensive gastropathy
Computerised tomogram liver abnormal	Portal shunt
Congestive hepatopathy	Portal shunt procedure

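### The SAP's term-based AESI tables leave out three events that protocol Table 9 names: alkaline phosphatase, total bilirubin and actinic keratosis

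*SAP*

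**What the plan says.** Protocol Table 9 has a liver group, introduced as "Elevated Liver Enzymes (reported as AESI if Grade" 2 or higher, with four entries: AST, ALT, alkaline phosphatase and total bilirubin. Its skin-cancer group applies at any grade and has five entries, among them "Actinic keratosis" and "Any other skin cancer".

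SAP 5.6.3 plans two kinds of AESI table. One follows the investigator's determination. The other is built from fixed lists of preferred terms and ignores the investigator's flag; the sentence that sets it up ends "designation of the reported event as an AESI will be summarized similarly". The lists are in Appendix 8.4, which opens with "This appendix outlines the definition of treatment-emergent AESIs", and the part that matters here, 8.4.1, is headed *Protocol-Specified AESIs*. For topics with both kinds of term, 5.6.3 adds: "Safety topics for which narrow and broad terms are identified, only narrow terms are used for summary tables".

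The hepatotoxicity list in 8.4.1.3 mixes narrow and broad terms and marks the narrow ones with a superscript. It contains "Blood alkaline phosphatase increased" and "Blood bilirubin increased", both unmarked. The list in 8.4.1.5 is titled Non-Melanoma Skin Cancers.

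SAP 8.4.1 gives a reason for leaving out ovarian toxicity, and SAP Section 6 (item IV) records a change to the electrolyte terms. Neither mentions alkaline phosphatase, bilirubin, actinic keratosis or melanoma.

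**The concern.** SAP 5.6.3 presents the safety topics as going beyond the AESIs in protocol Section 11.3.1, so a reader will expect the lists in 8.4.1 to contain at least the Table 9 events. For three of them they do not.

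The term-based tables give the incidence of each AESI topic without depending on whether an investigator ticked the AESI box. If these events occur, the hepatotoxicity and skin-cancer topics would be undercounted against the protocol's own list. A reader who takes the tables as the Table 9 AESIs could read a missing row as no events.

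**Working it through.** There is no planned figure to reproduce. The check matches each Table 9 entry to Appendix 8.4.1 and then applies the narrow-only rule. Entries are matched by wording, for example allergic reaction to the Hypersensitivity terms, and hidradenitis suppurativa to Hidradenitis.

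| Table 9 group | Entries | SAP list | Full route | Part | No route |
|---|---|---|---|---|---|
| Skin rash | 5 | 8.4.1.2 | 5 | 0 | 0 |
| Liver | 4 | 8.4.1.3 | 2 | 0 | 2 |
| Electrolytes | 3 | 8.4.1.4 | 3 | 0 | 0 |
| Drug reactions | 3 | 8.4.1.1 | 3 | 0 | 0 |
| Skin cancer | 5 | 8.4.1.5 | 3 | 1 | 1 |
| Total | 20 | | 16 | 1 | 3 |

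The six ovarian entries are set aside because the SAP gives a reason for omitting them.

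**Liver.** The list in 8.4.1.3 carries 18 narrow marks:
- 6 are ALT, AST or transaminase terms.
- 4 are gamma-glutamyltransferase or bile acid terms.
- The remaining 18 − 6 − 4 = 8 are other terms, such as Hepatotoxicity and Acute hepatic failure.

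The alkaline phosphatase and blood bilirubin terms are:
- Blood alkaline phosphatase, abnormal and increased (2).
- Blood bilirubin, abnormal, increased and unconjugated increased (3).
- Bilirubin conjugated, abnormal and increased (2).
- Hyperbilirubinaemia (1).

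That is 2 + 3 + 2 + 1 = 8 terms, of which 0 are marked. Bilirubin excretion disorder, Bilirubin urine present and Urine bilirubin increased are unmarked too, so there is no other way in. A topic limited to transaminases would not explain this, because gamma-glutamyltransferase and bile acid terms are narrow although Table 9 does not name them. The only topic whose list says that broad terms will also be presented is skin disorders (8.4.1.2).

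**Actinic keratosis.** The mechanism differs: the term is not dropped by the rule but was never listed. It is not among the 30 terms in 8.4.1.5, nor in any other Appendix 8.4 list.

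**Melanoma.** It falls under "Any other skin cancer" in Table 9. SAP 8.4.1.5 draws on a MedDRA group that excludes melanoma and says so in its title, so this exclusion is stated but not reconciled with Table 9.

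**Could another table fill the gap?** The liver stopping-criteria table in SAP 5.6.4 cannot: all six of its conditions require raised ALT, so an isolated alkaline phosphatase or bilirubin rise does not enter it.

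**The case against.** The strongest reply is that almost nothing is lost. SAP 5.6.2 already tabulates every treatment-emergent event by SOC and preferred term, by maximum grade and by preferred term alone, and none of that depends on the AESI flag. SAP 5.6.4 tabulates alkaline phosphatase and bilirubin values by CTCAE grade and by multiple of the upper limit of normal. Table 9 is also a reporting list for investigators, which the investigator-determined AESI table implements, and protocol 12.3.2 promises no AESI table. This stands, and it is why the point is minor. It does not remove the point. The general tables do not give the number of participants with any event in the hepatotoxicity or skin-cancer topic, and rows for single preferred terms cannot be summed because one participant may appear in several.

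It is also fair to say that the term-based topics were never an exact copy of Table 9, since 5.6.3 and 8.4.1.3 set no grade limit. That explains extra events in the tables, not missing types of event.

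Three stronger readings are tempting, and the documents support none of them:
- *These events go unreported.* They do not, for the reasons above.
- *The naevus syndromes in 8.4.1.5 show that the list is not confined to cancers, so its scope cannot explain the omission of actinic keratosis.* The stated source group covers malignant and unspecified neoplasms, and the SAP names only one addition to it. On that text the naevus syndromes come from the source group and show no inconsistency.
- *Other narrow marks are wrong, because Suspected drug-induced liver injury and Acute hepatic failure are marked while Drug-induced liver injury and Hepatic failure are not.* A superscript on a single term may have been lost when the text was read from the PDF, so this cannot be counted against the plan.

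**Conclusion.** The mismatch is real and minor. Two of the four liver entries and one of the five skin-cancer entries in Table 9 have no route into the term-based tables, and a fourth entry is covered except for melanoma. These are counts of list entries. A reader might turn 3 of 20 into a rate of missed events, but the documents do not allow that: the number of events or participants affected cannot be derived, and it is zero if no such events occur.

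The effect is confined to descriptive safety tables. The flag-independent incidence for two topics would be undercounted against the protocol's own list. No endpoint, hypothesis or decision changes.

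The liver part assumes that the narrow marks in the text are complete. Marks survive on other terms throughout the same list, so loss on every alkaline phosphatase and bilirubin term is unlikely, but the source file should be checked. The actinic keratosis and melanoma parts do not depend on those marks.

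**What to change.** 1. In SAP 8.4.1.3, mark as narrow Blood alkaline phosphatase abnormal and increased, Blood bilirubin abnormal and increased, and Hyperbilirubinaemia (five terms). The conjugated and unconjugated bilirubin terms (three) are optional, since Table 9 names total bilirubin only. Do not open the topic to all broad terms, which would bring in entries such as Hepatic cancer metastatic.
2. In SAP 8.4.1.5, add Actinic keratosis. Either add melanoma terms as well, or state that melanoma is reported only through the investigator-determined AESI table.
3. If any of these omissions is intended, give the reason in a sentence, as 8.4.1 does for ovarian toxicity.

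The cost is two edits to term lists and a rerun of existing tables. The drawback is that some of the added alkaline phosphatase or bilirubin events may reflect liver metastases rather than an effect of the drug, so the hepatotoxicity table should be read with that in mind.

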### **11.3.1. Adverse Events of Special Interest**

Adverse events of special interest (AESIs) are selected non-serious and serious AEs that must be reported regardless of relationship to study treatment.

Refer to [Table 9](#) for the AESIs identified for this study. AESIs will be followed until resolution or return to baseline.

Following medical evaluation, Sites may be contacted to provide supplemental information (such as medical history, concomitant medications, investigations, etc.) about the event. Please note this table lists known AESIs; additional events may be identified during the course of the study.

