8.4.1. Protocol-Specified AESIs

Ovarian Toxicity is specified in the protocol as an AESI. However, the majority of participants in this study will not menstruate since they have had their ovaries or uterus, or both, surgically removed, or were documented to be post-menopausal. Therefore, it will not be relevant to assess ovarian toxicity in this study so the Preferred Terms defining Ovarian Toxicity are not included in this section.

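### As marked, the term-based hepatotoxicity table cannot show bilirubin or alkaline phosphatase events, two of the four protocol liver AESIs, and its marks on some liver diagnoses are inconsistent

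*SAP*

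**What the plan says.** **Protocol.** Section 11.3.1 says that AESIs "must be reported regardless of relationship to study treatment". The liver group in Table 9 is headed "Elevated Liver Enzymes (reported as AESI if Grade" 2 or higher (CTCAE v5.0). It has four items: AST, ALT, "Alkaline Phosphatase" and "Total bilirubin".

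**SAP 5.6.3.** Two kinds of AESI summary are planned, each by system organ class (SOC) and preferred term. One follows the investigator's determination. The other is described as "and those by using defined lists of specific MedDRA PTs without regard to the" investigator's own designation. For topics with both kinds of term, the rule is "Safety topics for which narrow and broad terms are identified, only narrow terms are used for summary tables".

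**SAP 8.4.** The appendix opens with "This appendix outlines the definition of treatment-emergent AESIs". Hepatotoxicity (8.4.1.3) stands under the heading "8.4.1. Protocol-Specified AESIs". It is a custom query drawn from the narrow and broad terms of five standardised MedDRA queries, with narrow terms shown by a footnote mark.

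**Stated exceptions.** Section 8.4.1.2 says that skin disorders will be shown for narrow and broad terms. Section 8.4.1 gives a reason for leaving out ovarian toxicity. Section 6 records added electrolyte terms. None of these covers bilirubin, alkaline phosphatase or the Hepatotoxicity marks.

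**The concern.** The SAP presents this query as its definition of a protocol-specified AESI, and the narrow-only rule then decides what the table shows. If a protocol liver item has no narrow term, the term-based table cannot show it, whatever happens in the trial. The same applies to a liver diagnosis that is left unmarked while a near-equivalent is marked.

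The table matters because it does not depend on whether the investigator flagged the event. Protocol 4.3 lists elevated liver transaminases as an important identified risk, so readers will look here for the liver signal. A low count could be read as reassurance when it partly reflects which terms carry a mark. No estimand, primary result or stopping rule is involved.

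**Working it through.** The plan states no figure on this point, so the check is a reading of the list in SAP 8.4.1.3 against protocol Table 9.

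**Step 1: the list.** It has 315 distinct terms, of which 18 are marked narrow, leaving 315 − 18 = 297 unmarked. The 18 are:
- ALT abnormal and increased; AST abnormal and increased; gamma-glutamyltransferase abnormal and increased; transaminases abnormal and increased; bile acids abnormal and increased (10)
- Acute hepatic failure, Hepatotoxicity, Hepatitis toxic, Suspected drug-induced liver injury (4)
- Acquired factor V deficiency, Factor VII activity decreased, Anti-liver cytosol antibody type 1 positive, Liver-kidney microsomal antibody positive (4)

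**Step 2: the four protocol items.** One rule is used for all of them: count every listed term that names the analyte.

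| Table 9 item | Terms naming it | Narrow |
|---|---|---|
| ALT or AST | 7 | 4 |
| Total bilirubin | 9 | 0 |
| Alkaline phosphatase | 2 | 0 |

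Bilirubin and alkaline phosphatase together score 0 of 9 + 2 = 11. The four narrow ALT and AST terms are the standard *abnormal* and *increased* terms. The three unmarked ones are *Mitochondrial aspartate aminotransferase increased*, *AST/ALT ratio abnormal* and *AST to platelet ratio index increased*. The unmarked terms in the other two rows include *Blood bilirubin increased* and *Blood alkaline phosphatase increased*, which are the direct counterparts of the marked ALT and AST terms.

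**Step 3: diagnoses and general enzyme terms.**

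| Narrow | Not narrow |
|---|---|
| Suspected drug-induced liver injury | Drug-induced liver injury |
| Acute hepatic failure | Hepatic failure; Subacute hepatic failure |
| Transaminases increased | Hypertransaminasaemia |

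A suspected injury is counted and an established one is not.

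**Step 4: size.** SAP 5.8 reports 53 enrolled; the planned number is 43. If all of them are treated, one participant is 1/53 = 1.9% or 1/43 = 2.3%. This is the amount by which an affected SOC row, and any overall row, falls for each participant who has an unmarked term and no narrow term. A participant who also has a narrow term stays in any overall row, and in the SOC row if that term belongs to the same SOC. The SAP does not spell out an overall row.

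**The case against.** The best answer is that nothing is lost from the report.

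- A Grade 2 or higher bilirubin or alkaline phosphatase AESI is tabulated and listed under the investigator's determination (SAP 5.6.3).
- It is also in the treatment-emergent tables (5.6.2).
- SAP 5.6.4 summarises laboratory results by maximum CTCAE grade where available. It also gives shift tables in multiples of the upper limit of normal for ALT, AST, alkaline phosphatase and bilirubin. Neither depends on coded terms.
- Protocol Appendix A4-3 requires possible Hy's Law cases to be reported as serious adverse events.

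This stands, and it is why the point is minor. The liver stopping-criteria summary helps less, because all six criteria require raised ALT and an isolated bilirubin or alkaline phosphatase event does not enter it.

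A reader might infer that the investigator-based and term-based tables ought to agree, so that any difference exposes the error. The documents do not support that. The term-based table ignores the investigator's designation and states no grade threshold, so the two would differ even with corrected marks.

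A reader might also infer that every ALT and AST term is narrow. Step 2 shows that only the standard ones are.

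The sponsor may choose its own narrow terms in a custom query, and bilirubin and alkaline phosphatase are less specific in this disease: the case series in the protocol synopsis gives the liver as the main metastatic site (67%). That argues for medical review of such events. It does not explain why two items that the protocol itself made AESIs are absent from the table presented as their definition, when the omission of ovarian toxicity is explained.

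Finally, the marks are superscripts read from a PDF. They survive on neighbouring terms, and all 11 relevant terms lack one, so chance loss looks unlikely. It cannot be excluded.

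**Conclusion.** Wrong as written, minor. The narrow-only rule and the marks together keep two of the four protocol liver AESIs, and several liver diagnoses, out of the term-based hepatotoxicity table, and no reason is given.

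It would go too far to say that liver events are missing from the study report or that the safety conclusions are unreliable, because the other tables carry them. It would also go too far to say that every hepatitis or jaundice term must be narrow. That is a medical judgement on which the documents are silent.

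The number of affected participants is unknown and may be zero. The conclusion assumes that the extracted marks match the sponsor's source list and that the table shells, which are held in separate documents (SAP 8.3), do not override the rule. The percentages assume 53 or 43 treated participants.

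**What to change.** First check the marks in SAP 8.4.1.3 against the source list. If they are as read, mark these as narrow:

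- **Bilirubin and alkaline phosphatase (7):** Blood bilirubin increased, Blood bilirubin abnormal, Bilirubin conjugated increased, Blood bilirubin unconjugated increased, Hyperbilirubinaemia, Blood alkaline phosphatase increased, Blood alkaline phosphatase abnormal.
- **Injury, failure and enzymes (10):** Drug-induced liver injury, Liver injury, Hepatocellular injury, Hepatic failure, Subacute hepatic failure, Acute on chronic liver failure, Hepatic necrosis, Hepatitis fulminant, Hypertransaminasaemia, Hepatic enzyme increased.

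The narrow list then has 18 + 7 + 10 = 35 terms. Keep the narrow-only table, and leave the wider hepatitis and jaundice terms and the remaining unmarked terms to the sponsor's medical review.

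The cost is a list edit and a rerun of one table, with no new data. Hepatotoxicity counts may rise, and some bilirubin or alkaline phosphatase events may reflect liver metastases and need medical review before they are read as drug effects.
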